7.1. Screening Visit

The purpose of the screening visit/period is to ensure that appropriate patients are entered into the study and that they remain stable during the pre-treatment period.

- Obtain written informed consent/assent prior to performing any study procedures
- Review Inclusion/Exclusion Criteria
- Complete medical history/review of systems
- Review immunization record for adolescent patients
- Collect demographic information
- Measure vital signs
- Perform a complete physical examination, including height and weight

- Collect concomitant medication and procedure/therapy information
- Complete the following assessments: Investigator's Global Assessment (IGA), Body Surface Area (BSA), and Eczema Area and Severity Index (EASI)
- Draw blood samples for laboratory tests, including serum pregnancy
- Collect urine sample for urinalysis
- Assign eDiary and instruct the patient on the completion of the following assessments: Pruritus and Sleep-Loss (daily), and POEM (weekly)
- Instruct the patient to apply a moisturizer at least twice daily

7.2. **Baseline Visit (Day 1) Induction Period**

- Administer the DLQI/CDLQI and EQ-5D
- Administer the PROMIS (Patient-Reported Outcomes Measurement Information System): Anxiety and Depression measures
- Collect the ACQ-5 assessment for patients with comorbid asthma
- Update medical history/review of systems and concomitant medication and procedure/therapy information
- Complete the following assessments: IGA, BSA, EASI and SCORAD
- Review compliance report on the eDiary and confirm moisturizer use
- Measure vital signs
- Draw a pre-dose blood sample for PK and anti-drug antibody (ADA) testing
- Conduct urine pregnancy test (WOCBP only)
- Re-assess and confirm patient eligibility (Inclusion/Exclusion criteria)
- Randomize the patient, receive kit assignment, and administer study drug
- Remind patient to record the following: Pruritus and Sleep-Loss (daily), and POEM (weekly)

Sites collecting photos will also:

- Obtain written informed consent for collecting photos
- Select a target lesion and obtain a photograph

7.3. **Week 2 (\pm 3 Days)**

- Complete the following assessments: IGA, BSA and EASI
- Review and record AEs and update concomitant medication and procedure/therapy information
- Review compliance report on the eDiary, confirm moisturizer use and remind patient to record the following: Pruritus and Sleep-Loss (daily), and POEM (weekly)

- Measure vital signs
- Administer study drug

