6.3. Adjustments for Covariates

Unless otherwise specified, the statistical analysis models for the Induction Period efficacy and health outcome analysis will include the following stratification factors for Baseline randomization: geographic region (US versus EU versus rest of world), age (adolescent patients 12 to <18 versus adults ≥18 years) and baseline disease severity (IGA 3 versus 4).

The statistical analysis models for the Modified Maintenance Primary Population (Maintenance Blinded Period) efficacy and health outcome analysis will include geographic region (US versus EU versus rest of world). Below are the country allocations within each geographic region.

Below are the country allocations within each geographic region.

Table KGAC.6.5. Geographic Regions for Statistical Analysis

Geographic Region	Country or Countries
US	United States
Europe	Bulgaria, Germany, Ukraine
Rest of world	Canada, Mexico, Singapore, Taiwan

In general, when an MMRM is to be used for analyses, baseline value and baseline-by-visit interactions will be included as covariates; when an ANCOVA is to be used for analyses, baseline value will be included as a covariate.

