European Quality of Life-5 Dimensions-5 Levels (EQ-5D-5L)	EQ-5D comprises five dimensions: mobility, self-care, usual activities, pain/discomfort and anxiety/depression. The EQ VAS records the patient's self-rated health on a vertical visual analogue scale. The scores on these five dimensions can be presented as a health profile or can be converted to a single summary index number (utility) reflecting preferability compared to other health profiles	▪ EQ-5D mobility	Five health profile dimensions, each dimension has 5 levels: 1 = no problems 2 = slight problems 3 = moderate problems 4 = severe problems 5 = extreme problems	Each dimension is a single item, missing if missing.
		▪ EQ-5D self-care	It should be noted that the numerals 1 to 5 have no arithmetic properties and should not be used as a primary score.	
		▪ EQ-5D usual activities		
		▪ EQ-5D pain/discomfort		
		▪ EQ-5D anxiety/depression		
		▪ EQ-5D VAS	Single item. Range 0 to 100. 0 represents “worst health you can imagine” 100 represents “best health you can imagine”	Single item, missing if missing.
		Change from baseline in EQ-5D VAS	Change from baseline: observed EQ-5D VAS score – baseline EQ-5D VAS score	Missing if baseline or observed value is missing.

Measure	Description	Variable	Derivation / Comment	Imputation Approach if Missing Components
		EQ-5D-5L UK Population-based index score (health state index)	Derive EQ-5D-5L UK Population-based index score according to the link by using the UK algorithm to produce a patient-level index score between -0.59 and 1.0 (continuous variable).	N/A – partial assessments cannot be saved on the eCOA tablet.
		Change from baseline in EQ-5D-5L UK Population-based index score	Change from baseline: observed EQ-5D-5L UK score – baseline EQ-5D-5L UK score	Missing if baseline or observed value is missing.
		EQ-5D-5L US Population-based index score (health state index)	Derive EQ-5D-5L US Population-based index score according to the link by using the US algorithm to produce a patient-level index score between -0.11 and 1.0 (continuous variable).	N/A – partial assessments cannot be saved on the eCOA tablet.
		Change from baseline in EQ-5D-5L US Population-based index score	Change from baseline: observed EQ-5D-5L US score – baseline EQ-5D-5L US score	Missing if baseline or observed value is missing.

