		Supportive Estimand (Composite)	CMH analysis with NRI	mITT with Baseline DLQI score at least 4	Leb 250 mg Q2W vs PBO; Week 16 and all scheduled visits in Induction Period	Supplementary analysis
	Proportion of patients achieving ≥ 4 point improvement in DLQI in patients who had baseline DLQI score ≥ 4	Maintenance Supportive Estimand (Composite)	CMH with NRI	mMPP with baseline DLQI score at least 4	Leb 250 mg Q2W vs PBO; Leb 250 mg Q4W vs PBO; All scheduled visits in Maintenance Period	Secondary analysis

Measure	Variable	Estimand (Section 6.2)	Analysis Method (Section 6.1)	Population (Section 6.1.1)	Comparison/Time Point	Analysis Type
	Proportion of patients achieving ≥ 4 point improvement in DLQI in patients who had baseline DLQI score ≥ 4	NA	Descriptive statistics	Modified Maintenance W16 Escape Population with Baseline DLQI score at least 4	No comparisons. All scheduled visits in Maintenance Period	Secondary analysis
SCORing Atopic Dermatitis (SCORAD)	Change from baseline in SCORAD score	Supportive Estimand (Hypothetical)	ANCOVA with LOCF	mITT	Leb 250 mg Q2W vs PBO; Week 16 and all scheduled visits in Induction Period	Secondary analysis
	Percent change from baseline in SCORAD score	Maintenance Supportive Estimand (Hypothetical)	ANCOVA with LOCF	mMPP	Leb 250 mg Q2W vs PBO; Leb 250 mg Q4W vs PBO; All scheduled visits in Maintenance Period	Secondary analysis
		NA	Descriptive stats	Modified Maintenance W16 Escape Population	No comparisons. all scheduled visits in Maintenance Period	Secondary analysis
	Proportion of patients achieving SCORAD75	Supportive Estimand (Composite)	CMH analysis with NRI	mITT	Leb 250 mg Q2W vs PBO; Week 16 and all scheduled visits in Induction Period	Secondary analysis
	Proportion of patients achieving SCORAD90	Maintenance Supportive Estimand (Composite)	CMH with NRI	mMPP	Leb 250 mg Q2W vs PBO; Leb 250 mg Q4W vs PBO; All scheduled visits in Maintenance Period	Secondary analysis
		NA	Descriptive stats	Modified Maintenance W16 Escape Population	No comparisons. all scheduled visits in Maintenance Period	Secondary analysis

Measure	Variable	Estimand (Section 6.2)	Analysis Method (Section 6.1)	Population (Section 6.1.1)	Comparison/Time Point	Analysis Type

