	Percentage change in SCORAD (having achieved EASI-75 at W16) from baseline	Maintenance Supportive Estimand (Hypothetical)	ANCOVA with LOCF	mMPP who have achieved EASI-75 at Week 16	Leb 250 mg Q2W vs PBO; Leb 250 mg Q4W vs PBO; All scheduled visits in Maintenance Period	Secondary analysis
Patient-Oriented Eczema Measure (POEM)	Change from baseline in POEM score	Supportive Estimand (Hypothetical)	MMRM with observed data	mITT	Leb 250 mg Q2W vs PBO; Week 16 and all scheduled visits in Induction Period	Secondary analysis
		Maintenance Supportive Estimand (Hypothetical)	ANCOVA with LOCF	mMPP	Leb 250 mg Q2W vs PBO; Leb 250 mg Q4W vs PBO; all scheduled visits in Maintenance Period	Secondary analysis
	NA	Descriptive stats	Modified Maintenance W16 Escape Population		No comparisons. All scheduled visits in Maintenance Period	Secondary analysis
		Supportive Estimand (Composite)	CMH analysis with NRI	mITT	Leb 250 mg Q2W vs PBO; Week 16 in Induction Period	Secondary analysis

Measure	Variable	Estimand (Section 6.2)	Analysis Method (Section 6.1)	Population (Section 6.1.1)	Comparison/Time Point	Analysis Type
European Quality of Life-5 Dimensions-5 Levels (EQ-5D-5L)	Proportion of patients having no problem in each domain: • EQ-5D mobility • EQ-5D self-care • EQ-5D usual activities • EQ-5D pain/discomfort EQ-5D anxiety/depression	Maintenance Supportive Estimand (Composite)	CMH analysis with NRI	mMPP	Leb 250 mg Q2W vs PBO; Leb 250 mg Q4W vs PBO; Week 52 in Maintenance Period	Secondary analysis
	Change from baseline in • EQ-5D VAS • EQ-5D-5L UK Population-based index score • EQ-5D-5L US Population-based index score	Supportive Estimand (Hypothetical)	ANCOVA with LOCF	mITT	Leb 250 mg Q2W vs PBO; Week 16 and all scheduled visits in Induction Period	Secondary analysis
		Maintenance Supportive Estimand (Hypothetical)	ANCOVA with LOCF	mMPP	Leb 250 mg Q2W vs PBO; Leb 250 mg Q4W vs PBO; All scheduled visits in Maintenance Period	Secondary analysis
		NA	Descriptive stats	Modified Maintenance W16 Escape Population	No comparisons. All scheduled visits in Maintenance Period	Secondary analysis
	Change from baseline in PROMIS Anxiety score	Supportive Estimand (Hypothetical)	ANCOVA with LOCF	mITT	Leb 250 mg Q2W vs PBO; Week 16 and all scheduled visits in Induction Period	Secondary analysis

Measure	Variable	Estimand (Section 6.2)	Analysis Method (Section 6.1)	Population (Section 6.1.1)	Comparison/Time Point	Analysis Type

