Following the implementation of MCMC-MI imputation as specified in Section 6.4.1.1, the 25 data sets with imputations should be set together and sorted by imputation number. The following sections describe the processes for combining inferences for the individual imputed data sets into one inference for reporting. All calculations are performed in SAS software version 9.4.

Summarize Unadjusted Response Rate

The response rates, overall and by treatment arm, and their associated standard errors (SE) are computed for each imputed data set using PROC FREQ with the *riskdiff* option specified for the appropriate column in the TABLES statement. The response rates and SEs from the resulting output are combined across the 25 imputed data sets using PROC MIANALYZE, separately for each arm and the overall group.

Note that the estimate and 95% confidence interval (CI) bounds output by PROC MIANALYZE are percents (ie, they are in terms of the response rate). To obtain the number of responders, the estimated percentage is multiplied by the number of individuals in the analysis population and rounded to the nearest integer.

Compute Stratified Measures of Association

The common risk difference, common odds ratio (OR), and Cochran-Mantel-Haenszel (CMH) test statistic are computed for each imputed data set using PROC FREQ with the *riskdiff* option for the appropriate column (for risk difference) and the *cmh* option (for odds ratio and CMH test statistic) specified in the TABLES statement. Each of these analyses are stratified by geographic region, age group, and baseline disease severity via inclusion of these variables in the TABLES statement with the treatment and outcome variables.

Note that the PROC FREQ output corresponding to the Mantel-Haenszel method is used for the risk difference, and the output corresponding to the General Association statistic is used for the CMH statistic. PROC MIANALYZE is then called separately for each of these measures, with further details in the sections below.

Common Risk Difference

No transformation is necessary before using PROC MIANALYZE to combine the risk difference estimates and their associated SEs across the 25 imputed data sets. This procedure outputs an estimate of the common risk difference and the associated 95% CI bounds.

Common Odds Ratio

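### The EQ-5D 'no problem' comparison ignores baseline status on the same item, so it mixes becoming problem-free with staying problem-free and gives up some precision

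*SAP*

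**What the plan says.** SAP Table KGAC.6.11 describes the EQ-5D-5L as "Five health profile dimensions, each dimension has 5 levels", scored "1 = no problems 2 = slight problems" and so on. Table KGAC.6.12 then analyses the "Proportion of patients having no problem in each domain" with CMH and non-responder imputation (NRI) in the modified maintenance primary population (mMPP) at Week 52. An unlabelled row just above the EQ-5D heading gives the same method for the mITT population at Week 16. The table is broken in the copy I have, so assigning that row to the EQ-5D is an inference.

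Neither row carries a baseline condition. For the induction CMH analyses, SAP Sections 6.1.2 and 6.3 adjust for the randomisation factors, and Appendix 2 repeats them: "Each of these analyses are stratified by geographic region, age group, and baseline disease severity". For maintenance, Section 6.3 says the "efficacy and health outcome analysis will include geographic region (US versus EU versus rest of world") and names no other factor. Baseline status on the EQ-5D item appears in neither.

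That baseline exists. The Baseline Visit in Protocol Section 7.2 includes "Administer the DLQI/CDLQI and EQ-5D". The other EQ-5D analyses use theirs: the VAS and both index scores go through ANCOVA, and Section 6.3 states that "when an ANCOVA is to be used for analyses, baseline value will be included as a covariate".

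**The concern.** Being at level 1 at Week 16 can be reached in two ways. A patient may start with a problem and lose it, or may never have had one in that domain and remain so without rescue, discontinuation or missing data. The planned proportion adds the two together, and a reader of the table cannot separate them.

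Baseline status on an item is likely to be a strong predictor of later status on it. Leaving it out of the strata has two costs. Some precision is lost, and a chance imbalance in baseline status between arms passes directly into the comparison. The second cost is most exposed at Week 52, where region is the only adjustment and the re-randomised placebo arm is small.

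**Working it through.** **Calibration.** The plan states no power for any EQ-5D analysis. Its only power figure is for the primary endpoints (SAP Section 5.2): 96 versus 48, more than 95%, continuity-corrected chi-square. For IGA 0/1 (34.7% vs 7.7%, difference 0.27, 2:1, pooled rate 0.257), the uncorrected placebo size is [1.96·√(0.257·0.743·1.5) + 1.645·√(0.077·0.923 + 0.347·0.653/2)]² / 0.27² = 42.3. The continuity correction multiplies this by ¼·[1 + √(1 + 3/(42.3·0.27))]², giving 47.7, so 48. Power at 48 vs 96 is 95.2%, which agrees with the plan.

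**What the planned difference contains.** Let s be the share with no problem at baseline, q the success rate among them and p the success rate among the rest (L = lebrikizumab, P = placebo). The full-sample difference is s·(q_L − q_P) + (1 − s)·(p_L − p_P). With s = 0.75, a difference of 6.25 points can mean 25 points among patients with a problem and none among the others (0.25 × 25). It can equally mean 8.33 points among patients without a problem and none among those with one (0.75 × 8.33). The planned output does not tell these apart.

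**Effect of the stratum at Week 16.** About 400 patients at 2:1 gives 267 vs 133 (SAP Section 5.2; mITT is smaller by Site 5042). The values of s, p and q are assumptions. Take p = 55% vs 30% and q = 93% in both arms. Power is Φ(z − 1.96). In the stratified version each baseline stratum has weight w = n_L·n_P/(n_L + n_P).

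- s = 0.75, as planned: 0.835 vs 0.7725, z = 0.0625/√(0.835·0.165/267 + 0.7725·0.2275/133) = 1.46, power 31%.
- s = 0.75, stratified: weights 66.6 and 22.2; numerator 22.2 × 0.25 = 5.55; variance 4.34 + 4.94 = 9.27; z = 1.82, power 45%.
- s = 0.50, as planned: 0.74 vs 0.615, z = 0.125/0.0500 = 2.50, power 71%.
- s = 0.50, stratified: weights 44.4 each; numerator 11.10; variance 2.89 + 9.87 = 12.76; z = 3.11, power 87%.

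This approximation flatters the stratum, because it ignores the 3 × 2 × 2 = 12 design strata that baseline status would split into 24. I therefore simulated the CMH test with all strata (12,000 runs; assumed regions 40/30/30, adolescents 50/400, baseline IGA 3 in 60%):

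| Assumed Week 16 case | Planned CMH | Baseline status added |
|---|---|---|
| s = 0.75, q = 93% in both arms | 31–32% | 37% |
| s = 0.50, q = 93% in both arms | 71% | 83% |
| s = 0.75, q = 93% vs 85% | 80% | 87% |
| s = 0.85, q = 93% in both arms | 18% | 17% |
| No effect, s = 0.75 (type I error) | 5.0% | 5.0% |

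**Week 52.** If the 48.0% EASI-75 planning rate stands in for the responder share, 267 × 0.48 ≈ 128 patients are re-randomised 2:2:1, about 51:51:26. With 51 vs 26, region strata and p = 55% vs 30%, simulated power goes from 59% to 62% (s = 0.75, q = 85% vs 60%), from 11% to 11% (s = 0.75, q = 93% in both arms) and from 21% to 25% (s = 0.50, q = 93% in both arms).

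**The case against.** The strongest defence is that this is a state endpoint in randomised arms, so the test is valid. It estimates the effect on being problem-free without rescue or discontinuation. Other state endpoints in the SAP, such as IGA 0 and DLQI 0 or 1, are also defined without a baseline condition on the item. The listed EQ-5D endpoint is change from baseline, the VAS and index analyses adjust for baseline, and this row supports no confirmatory claim. All of that stands, and it keeps the point small. It does not explain why a collected baseline should go unused here.

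A reader might go further and infer that most of the sample cannot show benefit, that power is roughly halved, and that the analysis should be confined to patients with a baseline problem. The documents do not support this.

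- They give no baseline EQ-5D distribution, so 'most' has no basis, and the share would differ by domain.
- Patients with no baseline problem cannot improve on that item, but they can worsen. Under NRI they also fail through rescue, discontinuation or missing data (SAP Section 6.4.1.3) and, in maintenance, transfer to escape (Section 6.4.2.2). These failures can differ by arm.
- Halving is one point in an assumed range. With s = 0.75 and equal retention, full-sample power is 31% against 70% in the subset (67 vs 33, z = 2.49). With 93% vs 85% retention, the full sample has 77% by the same approximation and restriction would lose power.
- Restriction answers a different question. At Week 52 it would leave about 6 placebo patients per domain (25% of 26).
- The DLQI precedent, "mITT with Baseline DLQI score at least 4", concerns a 4-point change that a patient below 4 cannot achieve. The SAP also runs that analysis in unrestricted mITT.

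**Conclusion.** The point holds in limited form. The EQ-5D no-problem comparison omits baseline status on the same item, reports a mixture of improving and not worsening, and gives up precision available from collected data. That the baseline is unused follows directly from the SAP text; only the Week 16 row rests on reading a broken table.

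The size rests wholly on assumptions: the baseline share without a problem, the rate of becoming problem-free, and NRI failure by arm. Over the cases tried, the stratum changes Week 16 power by about 0 to +12 points and Week 52 power by about 0 to 4, with type I error unchanged. It gives essentially nothing when the share without a problem is very high. No primary or major secondary conclusion is affected.

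**What to change.** In Table KGAC.6.12, keep mITT and mMPP as the populations and add baseline problem in that domain (level 1 versus levels 2 to 5) to the CMH strata at Weeks 16 and 52. State how a missing baseline item is classified. The stratum deals with precision and chance imbalance but does not by itself separate the two outcomes. So also tabulate, descriptively, the proportion at level 1 by baseline status in each arm, in addition to the planned analysis and not in place of it.

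The cost is one line in the table and one descriptive display per domain; no new data are needed. Strata rise from 12 to 24 in induction and from 3 to 6 in maintenance, so some will be sparse. The adjusted odds ratio becomes conditional on baseline status and will not match an unadjusted one. SAP Version 5 was approved after the study team was unblinded to induction treatment, so a Week 16 change made at or after that version should be labelled accordingly. The re-randomised assignments were still blinded at that version.

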6.11.1. Primary Outcome and Methodology

The primary analysis of the study is to test the null hypotheses that lebrikizumab 250 mg Q2W is the same as placebo when evaluating the proportion of patients achieving IGA of 0 or 1 at Week 16 in the mITT population. For EMA, an additional null hypothesis is that lebrikizumab 250 mg Q2W is the same as placebo when evaluating the proportion of patients achieving EASI-75 at Week 16 in the mITT population.

The primary estimand for the primary analysis is described in Section 6.2.1.1. The missing data including those as a result of intercurrent events will be imputed using MCMC-MI based on missing at random assumption (Section 6.4.1.1).

A CMH test as described in Section 6.1.2 will be used for the comparisons. The odds ratio, the corresponding 95% CIs and p-value, as well as the treatment differences and the corresponding 95% CIs, will be reported.

Multiplicity controlled analyses will be performed on the primary and major secondary objectives to control the overall Type I error rate at a 2-sided alpha level of 0.05. A graphical approach will be used to perform the multiplicity controlled analyses as described in Section 6.6.

Primary outcome IGA 0/1 ad EASI-75 and their analysis are described in [Table KGAC.6.11](#).

6.11.2. Sensitivity Analyses of Primary Outcome

Sensitivity analyses are included to demonstrate robustness of analyses. Tipping point analysis as described in Section 6.4.1.2 will serve as the sensitivity analyses for primary outcomes.

Sensitivity and supplementary analyses for both primary and secondary endpoints are described in [Table KGAC.6.11](#) and [Table KGAC.6.12](#).

There will be no adjustment for multiple comparisons for additional analyses of the primary outcome.

6.11.3. Major Secondary Efficacy Analyses

Major secondary outcomes and their analyses are described in [Table KGAC.6.11](#) and [Table KGAC.6.12](#).

6.11.4. Other Secondary Efficacy Analyses

Other secondary outcomes and their analyses are described in [Table KGAC.6.11](#) and [Table KGAC.6.12](#).

6.12. Health Outcomes/Quality-of-Life Analyses

Analyses of POEM, DLQI, EQ-5D-5L, PROMIS, and ACQ-5 are described in [Table KGAC.6.11](#) and [Table KGAC.6.12](#).

